19.1. Ethical Review Board/Ethics Committee

All protocols and the patient informed consent forms must have the approval of a properly constituted committee or committees responsible for approving clinical trials. The ERB/IRB decision must contain approval of the designated investigator, the protocol (identifying protocol title and version number), and of the patient informed consent.

The ERB/IRB written, signed approval letter/form must contain approval of the designated investigator, the protocol (identifying protocol title and version number), and of the patient informed consent. Documentation of Ethics Committee approval must be sent to the ETOP Coordinating Office prior to enrolment of the first patient.

Any modifications made to the protocol must be submitted to the appropriate ERB/IRB for information or approval in accordance with local procedures and regulatory requirements and to Health Authorities if required.

Once approved or acknowledged by the appropriate ERB/IRB and by the Health Authorities (if required), the investigator shall implement the protocol modifications. Protocol modifications for urgent safety matters may be directly implemented following the instructions of ETOP.

19.2. Regulatory approval procedures

If applicable, in addition to the approval of the Ethics Committee according to national legislation, the protocol, other protocol related documents including patient information and informed consent and other documents as required locally must be submitted to and be approved by the health authority. Documentation of health authority approval must be sent to the ETOP Coordinating Office prior to Participating Centre activation.

19.3. Informed consent

Informed consent for each patient will be obtained prior to initiating any trial procedures in accordance with the “Patient Information and Informed Consent” (See Appendix I). One signed and dated copy of the informed consent must be given to each patient and the original copy must be retained in the investigator's trial records. The informed consent form must be available to monitors and in the case of data audits. Verification of signed informed consent and the date signed are required for inclusion to this trial.

The "Declaration of Helsinki" recommends that consent be obtained from each potential patient in biomedical research trials after the aims, methods, anticipated benefits, and potential hazards of the trial, and discomfort it may entail, are explained to the individual by the physician. The potential patient should also be informed of her/his right to not participate or to withdraw from the trial at any time. The process of obtaining the informed consent must be documented in the patient record.

If the patient is in a dependent relationship to the physician or gives consent under duress, the informed consent should be obtained by an independent physician. By signing this protocol, the investigator agrees to conduct the trial in accordance with Good Clinical Practice and the "Declaration of Helsinki."

ETOP recognises that each institution has its own local, national, and international guidelines to follow with regard to informed consent. Therefore, we provide a template information sheet and informed consent form (Appendix I), which can be edited to incorporate information specific to your institution. The template Patient Information Sheet and Informed Consent has been written according to ICH guidelines which state the Informed Consent should adhere to GCP and to the ethical principles that have origin in the "Declaration of Helsinki". The final version needs to receive the Institutional Review Board/ Local Ethics Committee approval in advance of its use. Centres need to send their locally modified PIS/IC to ETOP for review and approval before submitting to their Ethics Committee.

20. Governance and administrative issues

20.1. Final report

A final clinical trial report will be written and distributed to Health Authorities as required by applicable regulatory requirements.

20.2. Steering Committee

A Steering Committee will be constituted for this trial. The Steering Committee is responsible for maintaining the scientific integrity of the trial, for example, by recommending changes to the protocol in light of emerging clinical or scientific data from other trials. Membership will include the trial chair and co-chair, trial coordinators, trial statisticians, ETOP officials, representatives from some participating institutions and groups, and a representative from Boehringer Ingelheim.

20.3. Independent Data Monitoring Committee

The trial will be presented for review to the ETOP IDMC at each of their semi-annual meetings. Accrual and safety will be monitored. The Stage 1 Report will be reviewed by the IDMC which will make a recommendation to continue or stop the trial based on the results.

20.4. Publication

The results of the trial will be published according to the ETOP publication policy.

20.5. Clinical trial insurance

ETOP will contract the appropriate liability insurance for this trial. Patients who suffer injuries due to the trial should report them immediately to their physician. The local group/institution should report all alleged claims immediately to the ETOP Coordinating Office.

20.6. Quality Assurance

ETOP conducts trials according to the ICH Good Clinical Practice (GCP) guidelines. The Trial Data Manager reviews each CRF as it is received. In addition, the ETOP Medical Reviewer reviews each case at specific timepoints. ETOP conducts periodic audit visits to ensure proper trial conduct, verify compliance with GCP, and perform source data verification.

The Investigator should ensure that source documents are made available to appropriately qualified personnel from ETOP or its designees, or to Ethics Committee and health authority inspectors after appropriate notification.

At regular intervals during the clinical trial, the centre will be contacted, through monitoring visits, letters or telephone calls, by a representative of the monitoring team to review trial progress, investigator and patient compliance with clinical trial protocol requirements and any emergent problems. These monitoring visits will include but not be limited to review of the following aspects: patient informed consent, patient recruitment and follow-up, SAE documentation and reporting, AEs with pre-specified monitoring documentation and reporting, AE documentation, dispensing IP, compliance with protocol, drug accountability, concomitant therapy use, and quality of data.

20.7. Protocol adherence

Investigators ascertain that they will apply due diligence to avoid protocol deviations. Under no circumstances should the investigator contact ETOP or personnel monitoring the trial to request approval of a protocol deviation, as no deviations are permitted. The investigator should document and explain any deviations from the approved protocol. The investigator should promptly report any deviations to ETOP and to the EC concerned in accordance with the applicable EC policies and procedures. If the investigator feels a protocol deviation would improve the conduct of the trial this must be considered a protocol amendment, and unless such an amendment is developed and activated by ETOP and approved by the IRB/IEC/REB it cannot be implemented. All protocol deviations will be recorded.

20.8. Data protection

The samples and data collected will be coded to protect patient confidentiality. Each patient will have a unique identifier assigned by the RDE facility ETOPdata. Sites are responsible to keep a patient log locally in order to be able to link the unique identifier to the record of the patient.

Biological material will be assigned the same unique identifier. No identifiable / personal data will be stored in the trial database or the tissue repositories in the central lab.

Biological material will be transferred outside the treating institution for central review. Results of the assays will be coded only by the patient identifier.

Regulatory authorities and pertinent Ethics Committees (IRB/ERB) may have access to patient data on-site. ETOP audit or monitoring personnel will also have access to such data on-site.

## 1. INTRODUCTION

### 1.1 Preface

Afatinib presents a manageable toxicity profile and potentially offers a significant activity in terms of disease control and long-term outcome. Therefore this treatment option offers a good benefit to risk ratio in patients with HER2-mutate advanced NSCLC.

The primary objective of the study is to evaluate the ability of afatinib to control disease in pretreated patients with advanced NSCLC harbouring HER2 exon 20 mutations. More particularly, the primary endpoint is disease control at 12 weeks.

The secondary objectives of the study are:

- To evaluate secondary measures of clinical efficacy including progression-free survival (PFS),
- To assess the safety and the tolerability of the treatment.

### 1.2 History of the Study

ETOP/7-14 NICHE trial was activated in December 2014 and the first patient was enrolled on September 2015.

The ETOP IDMC reviewed the trial safety data during its scheduled bi-annually meetings, in April 2016 (n=5 patients enrolled; no safety issues identified) and October 2016 (n=13) when the interim analysis was presented. Follow-up was suspended based on the interim analysis and an unscheduled follow-up IDMC meeting in November 2016 on the 13 enrolled patients enrolled).

At the IDMC meeting of October 2016, the interim analysis (1st stage of Simon's two-stage design) was presented. Among the first 9 patients, 5 patients (55.6%) had not reached week 12 free of progression. Thus, the stopping threshold of the 1st stage of Simon's two-stage design was reached, since more than the maximum allowed of 3 patients had a progression by 12 weeks. Based on these results, the IDMC recommended suspending further recruitment into the trial while continuing the treatment and close follow-up for the enrolled patients.

A follow-up analysis, once all enrolled patients reached the 12-week assessment, was performed in November 2016. Among all 13 enrolled patients, 6 patients (46.2%) had not reached week-12 free of progression.

Based on the data and results of the interim analysis and considering the protocol specified early stopping rule, the IDMC recommended that:

- The ETOP 7-14 NICHE trial should be permanently closed to accrual.
- Treatment and follow-up of enrolled patients may continue based on the judgement of the treating physician.
- Patients should be informed.

### **1.3 Purpose of the present Statistical Analysis Plan**

The purpose of the present Statistical Analysis Plan (SAP) is to provide an analytic and solid framework for the final analysis of the patients enrolled in the NICHE study.

More details on the planned final evaluation in terms of methods, reporting conventions and formats are described in detail in the following sections.

The overall objectives and methods of the study, as dictated by its protocol, may be found in the Appendix.

## **2. GENERAL CONSIDERATIONS FOR THE ANALYSIS**

### **2.1 Timing of Analysis**

The final analysis will be performed at least six months after the last patient was enrolled and as soon as the database is formally locked.

### **2.2 Analysis Populations**

#### ***Interim evaluation Cohort***

The interim evaluation cohort will include the first 9 patients enrolled in the study, which were used for the evaluation of Simon's stage one.

#### ***Efficacy Cohort***

The efficacy cohort will include all eligible patients enrolled in the study until trial termination.

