#### ***Safety Cohort***

The safety cohort will encompass all eligible enrolled patients who have received at least one dose of trial treatment.

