# 3. SUMMARY OF STUDY DATA

## 3.1 MAIN OUTCOME

The primary endpoint according to study's protocol, is the **DCR**.

DCR will be calculated along with 90% exact binomial confidence interval (CI) for the efficacy cohort.

PFS and OS (medians and rates) will be estimated based on the product-limit Kaplan-Meier method, while the corresponding 95% CIs for the median values will be based on the complementary log-log transformation.

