## **4. EFFICACY ANALYSIS**

The primary efficacy analysis will include all eligible enrolled patients.

The primary endpoint is disease control, defined as complete or partial response or disease stabilisation lasting at least 12 weeks.

Results on the primary endpoint will be presented for the whole efficacy cohort as well as for the 'interim analysis' cohort.

Objective response, progression-free survival and overall survival, the secondary efficacy endpoints of the NICHE trial, will also be evaluated for the whole efficacy cohort.

Best overall response, defined as best response across all assessment time-points, during the period from enrolment to termination of trial treatment, and objective response rate, defined as the best overall response (complete or partial response) will be summarized in table format.

PFS (defined as the time between the minimum of enrolment and start treatment date until documented progression or death) and OS (defined as the time between the minimum of enrolment and start treatment date until death or last contact date for censored patients) will be summarized through tables as well as graphically depicted via Kaplan-Meier curves and alternative graphical illustrations if possible (spider plot, swimmer plot).

As an exploratory analysis, the association of the primary endpoint (Disease control at 12 weeks) with patients' baseline characteristics, prior treatments received as well as with translational results will be also investigated.

More particularly, the distribution of patients' baseline characteristics and prior treatments will be presented separately for the group of patients that achieved disease control at 12th week versus the group of patients that did not achieve disease control and corresponding Fisher's exact tests will be provided.

In a similar manner, all translational results will be presented separately for the groups of patients that achieved or not disease control. Also, PFS and OS results will be provided for selected subgroups of patients with particular interest (type of ERBB2 mutation, Gender and Smoking status). Log-rank test comparing the survival curves between subgroups will be also presented.

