| Results of HER2 central testing                                  | 5      | Efficacy cohort | HER2 (ERBB2) mutation   | Baseline                           | -                       | n (%)                          | NA   |                          |
| Section II: Follow-up & Treatment Administration      |        |                 |   |                                    |                         |                                |  |                          |
| Time on follow-up and Time on treatment                          | 6      | Efficacy cohort | No. of patients still on f-up, no. of discontinuations  | End of follow-up                   | -                       | n (%)
median, interq. range | Reverse Censoring based on OS (f-up)
Kaplan – Meier analysis (both) |                          |
| Reasons of treatment failures                                    | 7      | Efficacy cohort | Reasons of treatment failures   |                                    |                         | n (%)                          | NA   |                          |
| Section III: Analysis of Primary Endpoint                 |        |                 |   |                                    |                         |                                |  |                          |

| Table title  | Number | Population                                  | Endpoint                   | Time Points or how to conglomerate   | Covariates or Subgroups | Summary Statistics   | Formal Analysis         | Notes |
|--|--------|---|----------------------------|--|-------------------------|--|-------------------------|-------|
| Disease Control Rate (DCR) at 12 weeks   | 8      | Interim evaluation cohort & Efficacy cohort | Disease Control (Yes / No) | 12-week evaluation (tumor assessment)  | -                       | n (%)  | NA                      |       |
| Section IV: Analysis of Secondary Efficacy Endpoints                              |        |   |                            |  |                         |  |                         |       |

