| Best Overall Response and Objective Response Rate (ORR) for all enrolled patients (N=13) | 9      | Efficacy cohort                             | Best Overall Response, ORR | OR : The best overall response (CR or PR) across all assessment time-points according to RECIST Criteria 1.1, during the period from enrolment to termination of trial treatment. |                         | n (%)  |                         |       |
| Progression-free Survival (PFS) for all enrolled patients (N=13)                         | 10     | Efficacy cohort                             | PFS                        | PFS : time from the date of enrolment until documented progression or death without documented progression  | -                       | KM estimates: no. of patients, n(%) of PFS events, 12-week PFS (%) (95% CI), median PFS (in weeks) | Kaplan – Meier analysis |       |
| Overall Survival (OS) for all enrolled patients (N=13)                                   | 11     | Efficacy cohort                             | OS                         | OS : time from the date of enrolment until death  | -                       | KM estimates: no. of patients, n(%) of deaths, xx-weeks OS   | Kaplan – Meier analysis |       |

| Table title  | Number | Population      | Endpoint   | Time Points or how to conglomerate  | Covariates or Subgroups                      | Summary Statistics   | Formal Analysis         | Notes |
|--|--------|-----------------|--|---|--|--|-------------------------|-------|
|  |        |                 |  | from any cause  |  | (%) (95% CI), median OS (in weeks)   |                         |       |
| Section V: Translational Results                            |        |                 |  |   |  |  |                         |       |
| Translational results of central testing                           | 12     | Efficacy cohort | All biomarkers included in the central testing (wild-type, mutation detected, type of mutation detected) | Baseline  | -  | n (%)  |                         |       |
| Section VI: Exploratory Analysis of Efficacy Endpoints      |        |                 |  |   |  |  |                         |       |

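### The SAP limits the primary DCR and the safety cohort to eligible patients; this clashes with its own table titles and, for safety, with SAP 5 and protocol 17.3

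*SAP*

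**What the plan says.** **Efficacy.** SAP 2.2 defines the cohort thus: "The efficacy cohort will include all eligible patients enrolled in the study until trial termination". SAP 4 repeats the limit: "The primary efficacy analysis will include all eligible enrolled patients". SAP 3.1 ties the main result to it: "DCR will be calculated along with 90% exact binomial confidence interval (CI) for the efficacy cohort".

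Elsewhere the SAP describes the population differently:

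- Tables 9, 10 and 11 in the SAP 8 listing give the Efficacy cohort as their population, but their titles refer to everyone enrolled. The Table 10 title, for example, reads "Progression-free Survival (PFS) for all enrolled patients (N=13".
- Table 8, for the DCR, gives its population as "Interim evaluation cohort & Efficacy cohort" and states no N. The first of these cohorts has no eligibility condition: "The interim evaluation cohort will include the first 9 patients enrolled in the study".
- SAP 3.2 summarises baseline data for all enrolled patients, while Table 2 assigns those data to the Efficacy cohort.

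Protocol section 17 names no efficacy population. Section 17.2 counts patients entering the trial, 17.4 times the stage 1 look by the number evaluable, and 17.3 leaves the detail of the analysis to the SAP.

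**Safety.** SAP 2.2 says: "The safety cohort will encompass all eligible enrolled patients who have received at least one dose of trial treatment". SAP 5 and protocol 17.3 define the safety cohort as every patient who took at least one dose, with no mention of eligibility.

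**The concern.** Protocol 8.3 has eligibility verified before a patient is enrolled. The word *eligible* can therefore only act afterwards, by removing someone later judged to have been enrolled in error. The SAP does not say who makes that judgement, when, or on what data. The criteria also leave room for disagreement: the protocol summary and the SAP appendix require a platinum-refractory tumour, whereas protocol 7.1.4 accepts any earlier platinum-based chemotherapy for advanced disease.

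Timing adds to this. SAP 1.2 reports: "Among all 13 enrolled patients, 6 patients (46.2%) had not reached week-12 free of progression". The cohort was thus defined when each patient's week-12 status was already available, and an exclusion could not be made blind to its effect on the DCR. With 13 patients, each one carries visible weight in the estimate.

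For safety, a treated patient ruled ineligible would disappear from the adverse event tables under one SAP definition and remain in them under the other. Tables 18 to 25 name only the Safety cohort, so they do not settle which definition applies.

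**Working it through.** **Inputs**

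- SAP 1.2: 13 enrolled, 6 not progression-free at week 12; among the first 9, 5 not progression-free.
- SAP 3.1: 90% exact binomial interval.
- Protocol 17.2 and 17.4: unacceptable DCR 50%; stop after stage 1 if fewer than 6 of 9 have disease control.
- Assumption: progression-free at week 12 is taken as disease control.
- Assumption: the documents report no ineligible patient, so zero, one and two exclusions are shown as a range.

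**Step 1. Reproduce the SAP's figures.** 6/13 = 46.2% and 5/9 = 55.6%, as stated in SAP 1.2. The numbers controlled are then 13 − 6 = 7 and 9 − 5 = 4.

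**Step 2. DCR by denominator.** DCR = x/n. The Clopper-Pearson 90% limits are the 5% quantile of Beta(x, n − x + 1) and the 95% quantile of Beta(x + 1, n − x).

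| Assumed exclusions | x/n | DCR | 90% exact CI | Shift from 53.8% (points) |
|---|---|---|---|---|
| None | 7/13 | 53.8% | 28.7 to 77.6 | – |
| One failure | 7/12 | 58.3% | 31.5 to 81.9 | +4.5 |
| One success | 6/12 | 50.0% | 24.5 to 75.5 | −3.8 |
| Two failures | 7/11 | 63.6% | 35.0 to 86.5 | +9.8 |
| Two successes | 5/11 | 45.5% | 20.0 to 72.9 | −8.4 |
| One of each | 6/11 | 54.5% | 27.1 to 80.0 | +0.7 |

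The interval for 7/13 is 77.6 − 28.7 = 48.9 points wide, so the shift from one exclusion is small beside the sampling uncertainty. Every interval contains 50%.

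**Step 3. Stage 1 decision.** The interim cohort has no eligibility limit, and 4 of 9 is below 6. Had one of the nine been removed, the result would be 4/8 or 3/8, still fewer than 6 controlled.

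**Step 4. Safety.** Assume all 13 took at least one dose and one of them is later ruled ineligible. An adverse event seen only in that patient is reported as 1/13 = 7.7% under SAP 5 and protocol 17.3, and as 0/12 under SAP 2.2.

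**Step 5. Are the two efficacy descriptions compatible?** The SAP 2.2 cohort equals the population in the titles of Tables 9 to 11 only if all 13 were eligible. No sentence in the SAP says that. Table 8 draws on the same named cohort, so the uncertainty reaches the primary endpoint.

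**The case against.** The strongest reply is that the efficacy part departs from nothing. The protocol names no efficacy population and hands the detail to the SAP, and analysing eligible patients is a recognised choice in a single-arm phase II trial. This stands: the added limit is not in itself a breach of the protocol.

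A second reply is that the table titles show the authors treated the efficacy cohort and the 13 enrolled as the same people, so the word does no work. That is the most natural reading, and a DCR table with a smaller N would contradict Tables 9 to 11. But it is an inference, and Table 8 itself gives no N.

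Third, one obvious route to late ineligibility is closed. Protocol 7.1.6 requires only a locally documented *HER2* mutation, and protocol 8.2 accepts local testing for enrolment, so a discordant central result would not make a patient ineligible. This narrows the risk but leaves the other section 7 criteria open.

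Finally, the numerical effect is hypothetical, the absence of an eligibility limit from the interim cohort is natural for a record of the nine patients used at stage 1, and any DCR denominator below 13 could be seen against SAP 1.2. All of this is accepted and is why the point is graded minor. None of it answers the safety conflict, where the SAP contradicts both itself and the protocol.

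**Conclusion.** The concern holds, as a minor one. The safety cohort has two incompatible definitions in the SAP, and the one in SAP 2.2 departs from the protocol; this conclusion needs no assumption. On efficacy, the SAP's definition and its table titles are reconciled only by an unstated fact, and the definition leaves discretion over the denominator after outcomes were known.

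One exclusion would move the reported DCR up by 4.5 or down by 3.8 percentage points; two would place it anywhere from 45.5% to 63.6%. These sizes rest on reading 7 of 13 as controlled and on exclusions that the documents do not report. If all 13 were eligible, no figure changes. The futility decision is unaffected, and Table 8 plans no formal test.

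**What to change.** - **SAP 2.2 and SAP 4, efficacy:** define the efficacy cohort as all 13 enrolled patients, which matches the titles of Tables 9 to 11, and state N in Table 8.
- **Sensitivity analysis:** if any patient is judged ineligible, show the eligible-only DCR as a sensitivity row, with each exclusion tied to a named protocol section 7 criterion and to data recorded before treatment.
- **SAP 2.2, safety:** delete *eligible*, so that the definition agrees with SAP 5 and protocol 17.3.

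The cost is a few words and at most one extra table row, with no new data. The reported DCR could be slightly lower or slightly higher than an eligible-only figure.
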